9.1 Definitions

Unanticipated Problems Involving Risk to Subjects or Others:

Any incident, experience, or outcome that meets all of the following criteria:

- Unexpected in nature, severity, or frequency (i.e. not described in study-related documents such as the IRB-approved protocol or consent form, the investigators brochure, etc.)
- Related or possibly related to participation in the research (i.e. possibly related means there is a reasonable possibility that the incident, experience, or outcome may have been caused by the procedures involved in the research)
- Suggests that the research places subjects or others at greater risk of harm (including physical, psychological, economic, or social harm).

Adverse Event:

An **adverse event** (AE) is any symptom, sign, illness or experience that develops or worsens in severity during the course of the study (regardless if study-related). Intercurrent illnesses or

CONFIDENTIAL

This material is the property of the University of Pennsylvania. Do not disclose or use except as authorized in writing by the study sponsor

injuries should be regarded as adverse events. Abnormal results of diagnostic procedures are considered to be adverse events if the abnormality:

- results in study withdrawal
- is associated with a serious adverse event
- is associated with clinical signs or symptoms
- leads to additional treatment or to further diagnostic tests
- is considered by the investigator to be of clinical significance

Serious Adverse Event:

Adverse events are classified as serious or non-serious. A **serious adverse event** (SAE) is any AE that is:

- fatal
- life-threatening
- requires or prolongs hospital stay
- results in persistent or significant disability or incapacity
- a congenital anomaly or birth defect
- an important medical event

Important medical events are those that may not be immediately life threatening, but are clearly of major clinical significance. They may jeopardize the subject, and may require intervention to prevent one of the other serious outcomes noted above. For example, drug overdose or abuse, a seizure that did not result in in-patient hospitalization, or intensive treatment of bronchospasm in an emergency department would typically be considered serious.

All adverse events that do not meet any of the criteria for serious should be regarded as **non-serious adverse events**.

Adverse Event Reporting Period:

The study period during which AEs/SAEs will be reported is from the initiation of any study procedures until the end of the study. Any event(s) that the subject, or the subject's personal physician, believes might reasonably be related to participation in the study after the final time point will be assessed and reported as appropriate.

Preexisting Condition:

A preexisting condition is one that is present at the start of the study. A preexisting condition should be recorded as an adverse event if the frequency, intensity, or the character of the condition worsens during the study period.

Post-study Adverse Event:

All unresolved adverse events should be followed by the investigator until the events are resolved, the subject is lost to follow-up, or the adverse event is otherwise explained. At the last scheduled visit, the investigator should instruct each subject to report any subsequent event(s) that the subject, or the subject's personal physician, believes might reasonably be related to participation in this study.

Hospitalization, Prolonged Hospitalization or Surgery:

Any AE that results in hospitalization or prolonged hospitalization should be documented and reported as a SAE unless specifically instructed otherwise in this protocol. Any condition responsible for surgery should be documented as an AE if the condition meets the criteria for an AE.

Neither the condition, hospitalization, prolonged hospitalization, nor surgery are reported as an adverse event in the following circumstances:

CONFIDENTIAL

This material is the property of the University of Pennsylvania. Do not disclose or use except as authorized in writing by the study sponsor

- Hospitalization or prolonged hospitalization for diagnostic or elective surgical procedures for a preexisting condition. Surgery should **not** be reported as an outcome of an adverse event if the purpose of the surgery was elective or diagnostic and the outcome was uneventful.
- Hospitalization or prolonged hospitalization required to allow efficacy measurement for the study.
- Hospitalization or prolonged hospitalization for therapy of the target disease of the study, unless it is a worsening or increase in frequency of hospital admissions as judged by the clinical investigator.

9.2 Collection and Recording of Adverse Events

9.2.1 AE Collection Methods

All AEs and SAEs occurring during the study period will be captured through the methods described below:

1. **Open-Ended AE Form:** Participants will be asked an open-ended question about any symptom or medical event that may be related to their study participation. These events will be documented as **unanticipated (unexpected)** AEs unless they are otherwise outlined in the protocol or consent (i.e. related to withdrawal, assessments, etc.). The reporting period for each assessment will inquire about any event(s) or symptom(s) experienced since the last in-person visit. If a participant reports a symptom or medical event, they will be asked to rate the severity of the event utilizing the following severity scale: 0 (None=No Concerns), 1 (Mild=Issue does not interfere with usual daily activities), 2 (Moderate=Issue does interfere with some activities), and 3 (Severe=No normal activities are possible). Any report on the Open-Ended AE Form will require additional follow up per the AE documentation and internal reporting procedures outlined below in section 8.2.2.
2. **Spontaneous Assessment:** Once enrolled, participants will be instructed to inform the research team about any notable symptom or medical event/concern throughout their participation in the study. A participant may also request the Principal Investigator be consulted about any reported medical event or concern of any severity at any time throughout their participation.
3. An “AE Note” template will be available to the research staff to collect supporting AE information and will function as the source document. However, research staff may collect AE information on any source document available to them and transfer the relevant information to a formal AE Note at a later time. Any notable AE reported spontaneously will require additional follow up per the AE documentation and internal reporting procedures outlined below in section 8.2.2.

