9.2.2 AE/SAE Documentation and Internal Reporting Procedures

AE/SAE Documentation: At a minimum, follow-up information will include AE/SAE onset/resolution, description of event/course, severity, action taken, outcome, and possible relation to study participation.

Information surrounding AEs and SAEs will be initially recorded on the appropriate source document such as the SEC Form, an “AE Note” or SAE Form, and/or any document in which the AE/SAE information was originally recorded. All applicable AEs and SAEs will then be documented on a cumulative AE and SAE log maintained within the regulatory binder.

Completed documentation of applicable AEs will include the following information:

CONFIDENTIAL

This material is the property of the University of Pennsylvania. Do not disclose or use except as authorized in writing by the study sponsor

- Protocol Title and IRB#
- Subject Identifier
- Event Title
- Date Site Notified
- Event Start Date and Time
- Event Stop Date and Time
- Description of Event/Course (including sequelae)
- Severity:
 - None = No concerns
 - Mild = Side effect or issue does not interfere with usual daily activities
 - Moderate = Side effect or issue interferes with some activities
 - Severe = No normal activities are possible
- Relatedness to the study procedures (PI):
 - Unrelated = Definitely not related
 - Unlikely = Doubtfully related
 - Possibly = May be related
 - Probably = Likely related
 - Definitely = Related
- Expectedness per protocol and/or consent
 - Expected/Anticipated
 - Unexpected/Unanticipated
- Action(s) taken (if appropriate)
- Outcome (if appropriate)

Documentation of SAEs will include the following information on a standardized SAE Form:

- Protocol name and number
- Subject identifiers
- Demographic data
- Date Site Notified
- Date and time of SAE onset
- Date and time of SAE resolution, if available
- Course/Description of Event (including sequelae)
- Action Taken
- Outcome
- Follow-up plan
- Serious Status (What makes the event an SAE)
- Severity of the event
 - None = No concerns
 - Mild = Side effect or issue does not interfere with usual daily activities
 - Moderate = Side effect or issue interferes with some activities
 - Severe = No normal activities are possible
- Relatedness to the study procedures (PI):
 - Unrelated = Definitely not related

CONFIDENTIAL

This material is the property of the University of Pennsylvania. Do not disclose or use except as authorized in writing by the study sponsor

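### The scheduled adverse-event question is described with two different scopes, the narrower of which falls short of the plan's own AE definition, so minor events seen as unrelated may be under-captured

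*Combined protocol and SAP*

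**What the plan says.** Section 9.1 of the combined protocol and SAP defines an adverse event as "any symptom, sign, illness or experience that develops or worsens in severity during the course of the study (regardless if study-related". It adds that intercurrent illnesses and injuries count, and that a pre-existing condition counts if it worsens during the study.

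Section 9.2.1 opens with an undertaking: "All AEs and SAEs occurring during the study period will be captured through the methods described below". Two routes follow.

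- **Open-Ended AE Form.** "Participants will be asked an open-ended question about any symptom or medical event that may be related to their study participation". The description of the form in section 7.4.1 uses the same sentence. Later in the same item comes: "The reporting period for each assessment will inquire about any event(s) or symptom(s) experienced since the last in-person visit". This second sentence sets no relatedness condition.
- **Spontaneous Assessment.** Once enrolled, "participants will be instructed to inform the research team about any notable symptom or medical event/concern throughout their participation". On handling, the section states: "Any notable AE reported spontaneously will require additional follow up".

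Section 9.2.2 assigns relatedness to the Principal Investigator on a five-level scale whose lowest level is "Unrelated = Definitely not related".

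**The concern.** The definition is broad and the undertaking is to capture everything that meets it. The scheduled question, in the sentence that says what is asked, is limited to events that might be connected with taking part. A participant with a cold, a minor injury or a flare of an old complaint could reasonably take such a question as not asking about it. Those are events that section 9.1 expressly counts.

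Two things are at stake. The first is completeness: the AE log may be thinner than the definition implies, and a reader of the results would have no means of knowing by how much. The second is the order of judgement. The plan reserves causality for the Principal Investigator and provides a category for unrelated events. If relatedness is used to screen the question, some events may never reach that assessment.

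**Working it through.** No figure in the documents bears on this point and no formula applies. The check sets the passages side by side.

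**Step 1. Which events are in scope?** Section 9.1 includes events whatever their relation to the study. It does use a test of believed relatedness, but only for events arising after the final time point. During the study there is no such filter, and the unrelated level of the scale in section 9.2.2 confirms that unrelated events are meant to be recorded.

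**Step 2. How often is the form used?** Sections 7.2.3 to 7.2.9 list it at Days 6, 7, 11, 14, 17, 21 and 22, which is all seven visits after Intake. It is the only AE question scheduled at visits. The concomitant medication review could bring some events to light, but section 9.2.1 does not list it as an AE collection method.

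**Step 3. Which events does each route cover as worded?** All four kinds of event below are AEs under section 9.1. The *narrow* reading takes the sentence on possible relatedness as the scope of the form. The *wide* reading takes the reporting-period sentence as the scope.

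| Event | Form, narrow | Form, wide | Spontaneous route |
|---|---|---|---|
| Possibly related, notable | covered | covered | covered |
| Possibly related, not notable | covered | covered | not covered |
| Seen as unrelated, notable | not covered | covered | covered |
| Seen as unrelated, not notable | **not covered** | covered | **not covered** |

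**Step 4. What follows?** On the wide reading nothing is missed, but the sentence on possible relatedness is then wrong. On the narrow reading exactly one of the four kinds is left out of both routes: events that are not notable and that the participant regards as unrelated. The third kind then depends on the participant volunteering it. The documents do not say which reading applies, so staff working from them could ask either question.

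**Step 5. Can the loss be sized?** It cannot. That would need the share of AEs that are minor and seen as unrelated, and the rate at which participants leave them out when asked the narrow question. The documents give neither.

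**The case against.** The strongest case on the other side has five parts.

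- **The form's description also contains the broad wording.** The reporting-period sentence has no relatedness limit. A reader might infer from the other sentence alone that the form asks only about events the participant attributes to the study. The documents do not support that; the item is inconsistent, not clearly restricted. One can answer that the reporting-period sentence only sets the look-back window, but then the narrow scope stands. Either way the text needs reconciling.
- **The form is not in the documents.** They describe the question and do not reproduce it. What participants are actually asked may already be broad. This stands, and it limits the finding to the protocol text unless the form carries the same clause.
- **Nothing says the participant decides causality.** A reader might infer that relatedness is pre-judged by the participant. That is a natural inference from a self-report question about possibly related events, but only an inference: sections 9.2.2 and 9.3.2 leave the judgement to the Principal Investigator, and any report on the form triggers follow-up. Possible relation is also a low threshold. The documents do not show that symptoms such as cough or headache after starting a new inhaled product would be the ones missed.
- **There is a second route.** Spontaneous Assessment has no relatedness limit, so it is too strong to say that the plan will fail to capture unrelated events. It narrows the gap without closing it, because it is passive and confined to notable events.
- **The consequence is small.** No AE endpoint appears in the objectives (section 3), the outcome variables (section 7.4.3) or the analytic plan (section 7.5). Expedited reporting in section 9.3 concerns unexpected events that are suspected reactions or judged probably or definitely related, and a serious event would be notable on any ordinary reading. This stands.

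**Conclusion.** The point holds as an internal inconsistency with possible under-capture. The scheduled AE question is given two scopes. The narrower one falls short of the section 9.1 definition, and the spontaneous route does not fully make up the difference. The statement that all AEs and SAEs will be captured is therefore not fully supported by the methods listed beneath it.

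The exposure is confined to non-notable events that participants regard as unrelated, across the seven visits after Intake. Its size cannot be computed. The primary analysis, the secondary outcome and the sample size are untouched, so this is a low-priority wording correction to safety ascertainment.

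The conclusion rests on two assumptions: that the form or the staff asking the question follow the narrow sentence, and that some participants would take it as excluding events they think unconnected with the study. If the form already asks about any event, only the protocol text needs correcting. A reader might go further and conclude that AE counts in this study are under-ascertained. The documents do not establish that.

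**What to change.** In sections 7.4.1 and 9.2.1, delete the closing clause of the question's description, the one limiting it to events possibly related to participation. The question then covers any symptom or medical event since the last in-person visit, in line with the reporting-period sentence in the same item. Check the Open-Ended AE Form and make the same deletion there if it carries the clause. Leave relatedness to the existing five-level Principal Investigator scale in section 9.2.2, which needs no change.

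If the sponsor prefers to keep the narrower question, qualify the opening sentence of section 9.2.1 so that it no longer claims capture of all AEs and SAEs.

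The cost is one clause in two places, possibly a form revision, and some extra minor unrelated events to log and grade. Section 9.1 already counts those as adverse events.

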9.2.2 AE/SAE Documentation and Internal Reporting Procedures

AE/SAE Documentation: At a minimum, follow-up information will include AE/SAE onset/resolution, description of event/course, severity, action taken, outcome, and possible relation to study participation.

Information surrounding AEs and SAEs will be initially recorded on the appropriate source document such as the SEC Form, an “AE Note” or SAE Form, and/or any document in which the AE/SAE information was originally recorded. All applicable AEs and SAEs will then be documented on a cumulative AE and SAE log maintained within the regulatory binder.

Completed documentation of applicable AEs will include the following information:

CONFIDENTIAL

This material is the property of the University of Pennsylvania. Do not disclose or use except as authorized in writing by the study sponsor

- Protocol Title and IRB#
- Subject Identifier
- Event Title
- Date Site Notified
- Event Start Date and Time
- Event Stop Date and Time
- Description of Event/Course (including sequelae)
- Severity:
 - None = No concerns
 - Mild = Side effect or issue does not interfere with usual daily activities
 - Moderate = Side effect or issue interferes with some activities
 - Severe = No normal activities are possible
- Relatedness to the study procedures (PI):
 - Unrelated = Definitely not related
 - Unlikely = Doubtfully related
 - Possibly = May be related
 - Probably = Likely related
 - Definitely = Related
- Expectedness per protocol and/or consent
 - Expected/Anticipated
 - Unexpected/Unanticipated
- Action(s) taken (if appropriate)
- Outcome (if appropriate)

Documentation of SAEs will include the following information on a standardized SAE Form:

- Protocol name and number
- Subject identifiers
- Demographic data
- Date Site Notified
- Date and time of SAE onset
- Date and time of SAE resolution, if available
- Course/Description of Event (including sequelae)
- Action Taken
- Outcome
- Follow-up plan
- Serious Status (What makes the event an SAE)
- Severity of the event
 - None = No concerns
 - Mild = Side effect or issue does not interfere with usual daily activities
 - Moderate = Side effect or issue interferes with some activities
 - Severe = No normal activities are possible
- Relatedness to the study procedures (PI):
 - Unrelated = Definitely not related

CONFIDENTIAL

This material is the property of the University of Pennsylvania. Do not disclose or use except as authorized in writing by the study sponsor

- Unlikely = Doubtfully related
- Possibly = May be related
- Probably = Likely related
- Definitely = Related
- Clinical assessment of subject conducted at time of SAE (if appropriate)
- Results of any laboratory tests and/or diagnostic procedures (if appropriate)
- Autopsy findings (if appropriate)
- Concomitant medications and therapies (excluding treatment of event)
- Relevant Medical History (if appropriate)

Internal Reporting Procedures: All relevant follow-up information outlined above (see AE/SAE documentation) concerning applicable AEs, including all information regarding the occurrence of previously reported event(s), will be reported to the Study Coordinator (or other senior personnel) and Principal Investigator to determine a course of action (e.g. continue to monitor, reduce medication dose, stop medication), relatedness (causality) to the study, and expectedness (if not already established). This consult will be documented via email. The clinical course of each event will be followed until resolution, stabilization, or until it has been determined that the study treatment or participation is not (or unlikely) to be the cause.

SAEs that are still ongoing at the end of the study period must be followed up to determine the final outcome unless it has been determined that the study treatment or participation is not the cause. Any SAE that occurs after the study period and is considered to be possibly related to the study treatment or study participation should be recorded and reported immediately per this protocol.

9.3 Reporting of Serious Adverse Events and Unanticipated Problems

The reporting requirements of applicable SAEs and/or Unanticipated Problems including reportable AEs (see section 8.1 for definitions) to external entities are detailed in the following sub-sections:

9.3.1 Investigator reporting: notifying NCI and FDA

The following events/reports will be submitted to the FDA and NCI Project/Program Officer in a narrative format or on FDA Form 3500A:

- Unexpected fatal or life-threatening suspected adverse reactions (in relation to study-provided IQOS and HeatSticks) will be reported as soon as possible, but in no case later than 7 calendar days after the initial receipt of the information.

9.3.2 Investigator reporting: notifying the Penn IRB

This section describes the requirements for safety reporting by investigators who are Penn faculty, affiliated with a Penn research site, or otherwise responsible for safety reporting to the Penn IRB. The University of Pennsylvania IRB (Penn IRB) requires expedited reporting of those events related to study participation that are unforeseen and indicate that participants or others are at increased risk of harm. The Penn IRB will not acknowledge safety reports or bulk adverse event submissions that do not meet the criteria outlined below. The Penn IRB requires researchers to submit reports of the following problems within 10 working days from the time the investigator becomes aware of the event:

- Any AE (regardless of whether the event is serious or non-serious, on-site or off-site) that occurs any time during or after the research study, which in the opinion of the Principal Investigator is:

CONFIDENTIAL

This material is the property of the University of Pennsylvania. Do not disclose or use except as authorized in writing by the study sponsor

Unexpected (An event is “unexpected” when its specificity and severity are not accurately reflected in the protocol-related documents, such as the IRB-approved research protocol, any applicable investigator brochure, and the current IRB-approved informed consent document and other relevant sources of information, such as product labeling and package inserts.)

AND

Related to the research procedures (According to the Penn IRB standard operating procedures [SOPs], an event is “related to the research procedures” if the event is deemed **probably or definitely related to the procedures.**”)

Reporting Process:

Unanticipated problems posing risks to subjects or others as noted above will be reported to the Penn IRB using the form: “Unanticipated Problems Posing Risks to Subjects or Others Including Reportable Adverse Events” or as a written report of the event (including a description of the event with information regarding its fulfillment of the above criteria, follow-up/resolution and need for revision to consent form and/or other study documentation).

Copies of each report and documentation of IRB notification and receipt will be kept in the Clinical Investigator’s study file.

Reporting Deaths (more rapid reporting requirements):

Deaths that occur during the course of a research study and that are:

- **Unexpected; AND**
- **Related to the research study; AND**
- **When other participants are believed to be at an increased risk of harm**

Must be reported to the IRB within 3 days from the time the investigator becomes aware of the death.

